Due to the potency of IV ZA, adverse effects of the agent may occur. The most common side effects of ZA are an acute phase reaction involving fever (15%), myalgias (8%), flu-like illness (7%), headache (6%) and arthralgias (5%)^{61,62}. In rare cases, patients may experience noncardiac chest pain (1/3%). Because infusion of IV ZA can cause an increase in serum creatinine up to 30 days post treatment, the drug should be avoided in persons with creatinine clearance <35 mL/min. An association between atrial fibrillation and IV ZA use was observed in a large study of over 7000 patients⁶². The FDA subsequently conducted an investigation, comparing results of the prior trial to other studies of IV ZA, and concluded that no clear relationship could be identified between bisphosphonate use and atrial fibrillation⁶³. Both oral and IV bisphosphonates have been associated with osteonecrosis of the jaw (ONJ), but further review of the data by the American Dental Association found that incidence of ONJ is rare in post-menopausal women with osteoporosis but more common in those with monthly infusions for cancer treatment⁶⁴. This group recommended no special treatment beyond routine dental care for those using IV ZA for osteoporosis. Finally, several reports of low trauma fractures of the femur have been observed among patients primarily over age 60 who are prescribed chronic bisphosphonate treatment (2.5-8 years)^{61,65}. A recent cohort study of over 1.1 million patients by Dell et al. found that while duration of use of bisphosphonates was correlated with incidence of atypical femur fractures, (particularly beyond 5 years of use), no correlation with age and duration of use was found.⁶⁶ Because our study will involve only a single dose of ZA, we do not anticipate observing the above effect from the drug alone. Based on these new findings, we also believe that individuals ages 61-65 should not be excluded by age alone.

Previous Clinical Trials of Zoledronic Acid

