- Subjects will be assessed for participation in physical therapy and occupational therapy since receiving the study drug, as well as willingness to get study drug again via interview held 7 days following infusion.

E. Days 1, 3, 7, 14, Post-Drug Infusion

- Subjects will be assessed weekly for one month after study drug administration for known side effects of the drugs, including myalgias, fever, gastrointestinal disturbances, and flu-like symptoms.
- Laboratory values will be drawn for serum calcium, phosphate, and magnesium.

F. Month 1 Post Injury (+/-4 days)

- Subjects will be assessed weekly for one month after study drug administration for known side effects of the drugs, including myalgias, fever, gastrointestinal disturbances, and flu-like symptoms.
- Blood samples* for laboratory values will be drawn for s-CTX, IL-1 β , 25-OH vitamin D, serum calcium, intact parathyroid hormone, and Serum P1NP. *The total amount of blood drawn for all laboratory tests will be < 25 ml at each data collection session.

G. Month 2, 6 & 10 Post Injury

A patient questionnaire will be administered either in-person or by telephone. The questions cover:

- Any evidence or knowledge of bone fractures since the previous contact.
- Information about exercises and standing, including use of functional electrical stimulation (FES), such as how often and average daily duration.
- Supply of vitamin D and calcium tablets with reminder to bring pill bottles with them to clinic for follow up assessments and study sponsored refill of medications. At these follow up visits, pill counts will be done to assess their compliance with medication use.

H. Months 4 & 12 Post Injury

- Blood sample will be drawn for s-CTX, 25-OH vitamin D, serum calcium, intact parathyroid hormone. Serum P1NP will also be drawn at 4 months. The total amount of blood drawn for all laboratory tests will be < 25 ml at each data collection session.
- Complete neurological exam (at 12 months only)
- A patient questionnaire will be administered.
- DXA scan

I. Month 8 Post Injury

- Blood sample will be drawn for 25-OH vitamin D and serum calcium. The total amount of blood drawn for all laboratory tests will be < 25 ml at each data collection session.

J. Serum 25-OH Vitamin D Monitoring and Supplements

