We will compare the treatment and control groups for baseline characteristics using t-tests and Chi-square tests as appropriate. Specifically, we will compare age at injury, baseline FRAX fracture risk, sex and injury level (tetraplegia/paraplegia) distribution. The level of significance for all analyses will be 0.05.

2. Evaluation of Hypotheses

Specific Aim 1: To determine the short and long term effects of zoledronic acid on BMD values of the hip, distal femur, and proximal tibia in patients with acute SCI relative to patients receiving placebo.

The primary hypothesis is that subjects treated with zoledronic acid will have at least a 50% smaller percentage decline in BMD values for the hip, distal femur and proximal tibia at 4 and 12 months post-injury than control subjects.

Analysis: For each of the bone sites to be evaluated, a percent change from baseline ([baseline BMD – follow-up BMD]/baseline BMD) will be modeled using mixed effects linear regression. Fixed effects will be included for treatment assignment, time, treatment by time interaction, and baseline BMD level. A random intercept term will be included to account for correlation among repeated measurements from the same subject. Within this regression model, we will estimate the difference between treatment groups at 4 and 12 months and test for significance of this difference. If the outcome of percent change is not normally distributed, we will apply an appropriate transformation (e.g., log, logit). If the necessary transformation is too complex for interpretation, we will consider using rank-based methods.

Secondary hypothesis 1 is that subjects treated with zoledronic acid will maintain original BMD values for the hip, distal femur and proximal tibia at 4 months and lose no more than 5% at 12 months post-injury.

Analysis: We will estimate the mean percent change at 4 and 12 months for the active treatment group along with associated 95% confidence intervals from the results of the mixed effects regression. BMD values at 4 months will be considered equivalent to those at baseline if the bounds of the confidence interval are within +/-2%. At 12 months, we will test the one-sided null hypothesis that the percentage decline is greater than 5% vs. the alternative that it is less than or equal to 5%.

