Specific Aim 3: To determine the safety and tolerability of early administration of intravenous zoledronic acid in persons with acute SCI. We expect to see only minor, transient side effects from zoledronic acid. *To evaluate this we will test the hypotheses that compared to controls, subjects treated with zoledronic acid will have (3a) an increased incidence of myalgias, fever, gastrointestinal disturbances, and flu-like symptoms over the three days after infusion of study drug; (3b) be less likely to participate in physical and occupational therapy during the first week after infusion, and (3c) be less likely to want the treatment again.*

Analysis: For each outcome, we will estimate group-specific rates (proportions) along with exact binomial confidence intervals. Comparisons between groups will be performed using Fisher's exact test.

References Cited

1. National Institute on Disability and Rehabilitation Research. Notice of Final Long-Range Plan for Fiscal Years 2005-2009. *Federal Register*. 2006;71(31):8166-8200.

8. Ashe MC. Bone Health Following Spinal Cord Injury. *Spinal Cord Injury Rehabilitation Evidence*. Ed. J. J. Eng et al. 2010. 1-26.

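### Hypothesis 3b is analysed as a yes/no over the first week with no stated threshold or measure of amount, so a null result would say little about lost therapy time

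*Combined protocol and SAP*

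**What the plan says.** Specific Aim 3 (sections B and E.2) carries three hypotheses. The second, 3b, is that ZA patients will "be less likely to participate in physical and occupational therapy during the first week after infusion". One analysis paragraph in E.2 serves all three: "For each outcome, we will estimate group-specific rates (proportions) along with exact binomial confidence intervals", and "Comparisons between groups will be performed using Fisher's exact test". Section E.1 sets the level: "The level of significance for all analyses will be 0.05".

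Collection is described in D.3, item 4, under the days 1-7 post-infusion heading: "Subjects will be assessed for participation in physical therapy and occupational therapy since receiving the study drug". The same sentence goes on to willingness to receive the drug again and ends with an "interview held 7 days following infusion".

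None of these places says what makes a patient a participant or a non-participant, and none asks for a number of days or sessions. On the effect itself, E.2 says "We expect to see only minor, transient side effects from zoledronic acid", and hypothesis 3a looks for symptoms over three days.

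**The concern.** The plan expects a short, early reaction. If that reaction costs therapy, it will mostly cost part of a week: an affected patient misses some early sessions and attends later ones. A single yes/no for the week registers such a loss only if the cut-point happens to fall in the right place, and no cut-point is given.

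Lost rehabilitation time is the practical price of dosing this early, and 3b is the hypothesis that addresses it. An unstated cut-point leaves the result dependent on a choice that could be made late. A non-significant result could then be taken as reassurance that the data do not give.

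**Working it through.** **The plan's own figures.** The plan gives no rate, power or sample size for 3b. Its totals of 24, 33 and 39 (D.3, item 1) concern bone density. They reproduce with the noncentral t at 2:1, 80% power and two-sided 5%, and do not bear on 3b.

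**Inputs from the documents.** 48 patients at 2:1 gives 32 ZA and 16 placebo; alpha is 0.05; the test is Fisher's (sidedness is not stated for Aim 3, so two-sided is assumed). Section C, on side effects, cites 15% for fever, 8% for myalgia and 7% for a flu-like illness.

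**Assumptions, not in the documents.** Seven therapy days; a background chance of missing any day, equal in both arms; a share q of ZA patients who also lose the first 2-3 days.

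**Step 1: any therapy versus none.** Take 70% daily attendance, three days lost and q = 50%.
- Placebo: P(any attendance) = 1 - 0.3^7 = 0.9998.
- Affected ZA patient: 1 - 0.3^4 = 0.9919.
- ZA arm: 0.5 x 0.9919 + 0.5 x 0.9998 = 0.996.

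Both arms sit at the ceiling. With 0/16 non-participants on placebo, Fisher needs at least 8/32 on ZA: the ZA-side tail is C(32,8)/C(48,8) = 0.0279, and adding the opposite tail of 0.0115 gives p = 0.039. That is 25% of the ZA arm with no therapy all week. Power is 0.00 in every scenario below.

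**Step 2: other definitions, same week.** Simulated power, 3,000 trials per scenario, 10% background absence:

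| Share of ZA affected | Fisher: no therapy all week | Fisher: any day missed | Fisher: 2 or more days missed | Mann-Whitney: days missed |
|---|---|---|---|---|
| 15% | 0.00 | 0.06 | 0.12 | 0.12 |
| 30% | 0.00 | 0.13 | 0.36 | 0.39 |
| 50% | 0.00 | 0.32 | 0.79 | 0.83 |
| 70% | 0.00 | 0.65 | 0.98 | 0.99 |

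At 50% affected, moving background absence from 5% to 20% takes the two-or-more-days rule from 0.96 to 0.41 and the day count from 0.91 to 0.68.

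**Step 3: lower attendance.** With 50% affected, 70-85% attendance and either two or three days lost, weekly Fisher power runs from about 0.05 to 0.92 across cut-points of one to three missed days. The Wilcoxon test on days attended in the same week gives 0.43-0.85 and needs no cut-point. Only a cut-point matched to the number of days lost beats it.

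**Step 4: what an amount would report.** At 10% background absence and an average of 2.5 days lost, the mean loss is q x 2.5 x 0.9 days.
- q = 50%: 1.125 days, or 1.125/7 = 16 percentage points of attendance.
- q = 15%: 0.34 days, or 5 points.

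The any-versus-none proportion shows essentially no difference in either case.

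**The case against.** A reader might infer that patients who lose two or three days are counted as participants under the plan, so that 3b must come out null. The documents do not support this. They state no any-versus-none rule, and a rule such as two or more days missed is also a yes/no suited to Fisher's test. Step 2 gives that rule nearly the power of the day count at 10% background absence (0.79 v 0.83 with half the ZA arm affected). The proportion and the Fisher test are therefore not fatal in themselves.

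It would also be unfair to set a weekly Fisher test against a Wilcoxon test on days 1-3, because window and scale then change together. Within days 1-3, with half the ZA arm affected, Fisher on two or more days missed (0.69-0.92) and Wilcoxon (0.72-0.92) are about equal. The comparisons above therefore stay within the week that 3b names.

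Three further points stand:
- The day-7 interview may govern only willingness to repeat, and the data collection forms in Appendix B, which are not in the documents, might hold a coding rule.
- At the cited 15% fever rate no method has useful power.
- The symptoms are captured directly under 3a, and the plan gives exact intervals as well as p-values.

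What remains is that the plan as written fixes neither a threshold nor an amount, and the informativeness of 3b depends heavily on which is used. An attended-over-scheduled ratio could also hide loss if unwell patients are not scheduled; the fix covers this.

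**Conclusion.** The point holds as a cheap improvement. An effect the plan expects to be transient is judged by a weekly yes/no with no stated threshold. Power against a 2-3 day loss is about 0 on the plainest reading. With half the ZA arm affected and 70-85% attendance, it is about 0.05 to 0.92 on other cut-points, against 0.43-0.85 for a count of days over the same week.

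These figures rest on assumed attendance, reaction shares and days lost. At a 15% reaction share power is about 0.1 whatever the method, so the benefit there is an estimate of therapy time lost with its uncertainty, not a better chance of significance. This is a secondary tolerability outcome, with no bearing on the primary analysis.

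**What to change.** Before unblinding, define 3b as PT/OT days or sessions attended out of those planned, over days 1-7 as the main window and days 1-3 as supportive. Count sessions withheld for illness as missed. Record attendance at the existing daily contacts (days 1-3) and the day-7 contact, or take it from therapy notes.

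Compare arms with a Wilcoxon or permutation test and report the difference in mean percent attended with a 95% CI. The proportion with Fisher's test can stay as a supplement at one pre-specified cut-point. Keep the day-7 interview for willingness to repeat.

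The cost is a little data abstraction, one week each for up to 48 patients, and a few lines of text. Some patients may still be on acute floors, so the source of attendance data should be named for each setting.
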